### **Cardiovascular events**

Cardiovascular (CV) events will be monitored in the study population and an independent CV adjudication committee will review events (See Section 6.4.10). CV events will be analyzed in conjunction with CV events observed in other Phase II and Phase III dapagliflozin studies and reported elsewhere.

#### **6.4.4 Reporting of serious adverse events**

Investigators and other study site personnel must inform appropriate AstraZeneca representatives via the web based data capture (WBDC) system of any SAE that occurs in the course of the study within 1 calendar day (ie, immediately but no later than the end of the next business day) of when he or she becomes aware of it. Follow-up information on SAEs must also be reported by the investigator with the same time frame.

The AstraZeneca representative will work with the investigator to compile all the necessary information and ensure that all the necessary information is provided to Bristol-Myers Squibb Global Pharmacovigilance and Epidemiology within one calendar day of initial receipt for fatal and life threatening events and within three calendar days of initial receipt for all other SAEs.

All SAEs have to be reported, whether or not considered causally related to the investigational product, or to the study procedure(s). All SAEs will be recorded in the eCRF. SAEs will be recorded from the time of informed consent.

The investigator and/or Sponsor are responsible for informing the Ethics Committee about the SAE as per local requirements. Reporting of SAEs to the Regulatory Authority is the responsibility of Bristol-Myers Squibb.

Investigators or other site personnel send automated email alert to the designated AstraZeneca representative (when the page with SAE information is saved in WBDC system).

If the WBDC system is not available, then the Investigator or other study site personnel reports by fax an SAE to the appropriate AstraZeneca representative. A paper back-up SAE report is used for this purpose. The same reporting time frames still apply. The investigator is responsible for completing the eCRF as soon as the system becomes available again. The AstraZeneca representative will forward all information relevant to the SAE to Bristol-Myers Squibb Pharmacovigilance via fax or email.

#### **6.4.5 Laboratory safety assessment**

Blood and urine samples for determination of clinical chemistry, haematology, coagulation and urinalysis will be taken at the times indicated in the Study Plan (see [Table 3](#)).

The date and time of sampling will be recorded on the laboratory requisition form. The samples will be processed by a central laboratory and results will be reported back to the clinic within 72 hours.

Due to the fasting laboratory assessments, patients will be instructed to abstain from all food and beverages for 12 hours prior to each clinic visit (drinking water is allowed).

On the morning of the clinic visit, investigational products and all other medications including anti-hypertensive, lipid lowering and anti-platelet agents, oral anti-diabetic drugs and insulin may not be taken at home. Patients should bring all their medication including anti-hypertensive medication and study drug, if applicable, to the site. Anti-hypertensive medication can be taken with a glass of water immediately after completion of blood pressure and body weight measurements. After blood and urine sample collection has been completed, patients can take their medications including oral anti-diabetic drugs, insulin, lipid-lowering and anti-platelet agents within 30 minutes before breakfast.

Patients should not drink alcohol within 24 hours prior to each visit and should not use tobacco/nicotine within 12 hours prior to each visit.

All samples should be taken by adequately trained study personnel and handled in accordance with instructions in the laboratory manual. Up to date reference ranges will be provided during the study and laboratory results will be compared to the laboratory standard normal ranges and flagged if they are outside the normal range. The Investigator should make an assessment of any clinically significant abnormalities in the laboratory reports. The laboratory reports should be signed, dated and retained at the study site as source data for laboratory variables.

For information on how AEs based on laboratory tests should be recorded and reported, see [Section 6.4.3](#).

The complete list of safety laboratory variables is displayed in [Table 9](#):

**Table 9 Safety Laboratory Variables**

Visit	1	2	3	4	5	6	7	8	9	10	11	12	13	14	15	16	17	18	Resci)
Study Week	-5	-4	-2	0	1	4	8	16	24	28	36	44	52	65	78	91	104	107	
Haematology																			
Haemoglobin	X			X	X	X	X	X	X	X	X	X	X	X	X	X	X	X	X
Haematocrit	X			X	X	X	X	X	X	X	X	X	X	X	X	X	X	X	X
Red blood cell count	X			X	X	X			X				X		X		X	X	X
White blood cell count and differential	X			X	X	X			X				X		X		X	X	X
Platelet count	X			X	X	X			X				X		X		X	X	X
Clinical chemistry (serum)																			
Aspartate Aminotransferase (AST, SGOT)	X			X	X	X	X	X	X	X	X	X	X	X	X	X	X	X	X
Alanine Aminotransferase (ALT, SGPT)	X			X	X	X	X	X	X	X	X	X	X	X	X	X	X	X	X
Alkaline Phosphatase (AP)	X			X	X	X	X	X	X	X	X	X	X	X	X	X	X	X	X
Lactate dehydrogenase	X			X	X	X	X	X	X	X	X	X	X	X	X	X	X	X	X
Creatine Kinase (CK)	X			X	X	X	X	X	X	X	X	X	X	X	X	X	X	X	X
Total Bilirubin (TB) a	X			X	X	X	X	X	X	X	X	X	X	X	X	X	X	X	X

Visit	1	2	3	4	5	6	7	8	9	10	11	12	13	14	15	16	17	18	Resc	
Study Week	-5	-4	-2	0	1	4	8	16	24	28	36	44	52	65	78	91	104	107		
Blood Urea Nitrogen (BUN)	X			X	X	X	X	X	X	X	X	X	X	X	X	X	X	X	X	X
Electrolytes: (- Sodium - Bicarbonate - Potassium - Chloride - Calcium - Magnesium - Phosphorus)	X			X	X	X	X	X	X	X	X	X	X	X	X	X	X	X	X	X
Total protein	X			X					X	X			X		X		X	X	X	X
Albumin	X			X					X	X			X		X		X	X	X	X
Uric acid	X			X		X	X	X	X	X	X	X	X	X	X	X	X	X	X	X
Serum Creatine (SCr)	X			X		X	X	X	X	X	X	X	X	X	X	X	X	X	X	X
Calculated creatinine clearance (Cockcroft-Gault formula) b	X			X		X	X	X	X	X	X	X	X	X	X	X	X	X	X	X
Estimated Glomerular Filtration Rate (MDRD formula)	X			X		X	X	X	X	X	X	X	X	X	X	X	X	X	X	X
Serum Cystatin C				X					X	X			X		X		X	X	X	X

Visit	1	2	3	4	5	6	7	8	9	10	11	12	13	14	15	16	17	18	Resc h)
Study Week	-5	-4	-2	0	1	4	8	16	24	28	36	44	52	65	78	91	104	107	
Serum Bone Metabolism Marker (Parathyroid Hormone (PTH), osteocalcin, 25 hydroxy-vitamin D, 1,25 dihydroxy-vitamin D)				X					X	X			X		X		X	X	X
FSH	X																		
TSH, Free T4 c)	X			X															
Hepatitis Screen Panel d)	X																		
Central Laboratory Urinalysis																			
Glucose e)	X			X	X	X	X	X	X	X	X	X	X	X	X	X	X	X	X
Blood by dipstick f)	X			X	X	X	X	X	X	X	X	X	X	X	X	X	X	X	X
pH	X			X	X	X	X	X	X	X	X	X	X	X	X	X	X	X	X
Albumin	X			X	X	X	X	X	X	X	X	X	X	X	X	X	X	X	X
Creatinine	X			X	X	X	X	X	X	X	X	X	X	X	X	X	X	X	X
Calculated Urinary albumine:creatinine ratio (UACR)	X			X	X	X	X	X	X	X	X	X	X	X	X	X	X	X	X

Visit	1	2	3	4	5	6	7	8	9	10	11	12	13	14	15	16	17	18	Resc	
Study Week	-5	-4	-2	0	1	4	8	16	24	28	36	44	52	65	78	91	104	107		
Local Urinlysis																				
Pregnancy test g)	X	X	X	X	X	X	X	X	X	X	X	X	X	X	X	X	X	X	X	X
Urine Culture at local laboratory at unscheduled visit h)																				

- a) Both direct and indirect bilirubin will be reported if Total Bilirubin >1.5 X ULN.
- b) Creatinine clearance will be calculated by the method of Cockcroft and Gault. See Section 5.8. and Appendix K for details.
- c) Free T4 will be measured only if TSH is outside of normal range.
- d) Includes Hepatitis B viral antibody IgM, Hepatitis B surface antigen and Hepatitis C virus antibody.
- e) Results will be blinded.
- f) Microscopy if dipstick positive for blood.
- g) Urine HCG pregnancy test for WOCBP (HCG minimum sensitivity of 25 IU/L) (dipstick analyzed at the study centre).
- h) Refer to Section 6.4.9.2. (urinary and genital infections). In the event of patient reported signs and/or symptoms suggestive of an infection, a urine sample will be collected for culture at a subsequent unscheduled visit.
- i) Rescue refers to Glycaemic Rescue Visit (Section 5.6.2.1). In case of a Rescue Visit due to Hypertension (Section 5.6.2.4), it will be at the discretion of the investigator to decide if any laboratory assessments are needed.

Efficacy laboratory samples are indicated in [Table 8](#).

For blood volume see Section [7.1](#).

#### **6.4.6 Physical examination**

- A brief physical examination should include the cardiovascular system, lungs, abdomen, and extremities, and any organ system pertinent to the patient's signs, symptoms, or AEs. The patient should always be evaluated for the presence of oedema.
- A complete physical examination should include general appearance, head, eyes, ears, nose, throat, neck, cardiovascular system, lungs, abdomen, lymph nodes, extremities, neurological system, skin, and musculoskeletal system. The patient should always be evaluated for the presence of oedema.

Baseline data is collected at Visit 1, and new findings discovered on subsequent physical examinations should be recorded as changes from baseline.

#### **6.4.7 ECG**

A 12-lead ECG will be taken (supine position, standard ECG with a recommended paper speed of 50 mm/second covering at least 6 sequential beats) after the patient has been lying down resting for at least 5 minutes. Heart rate, QRS durations, PR, QT and QTc intervals will be recorded from standard lead of the computerised ECG and will be entered in the eCRF. The ECG will be evaluated by the investigator and entered as 'Normal' or 'Abnormal' in the eCRF. If the ECG is evaluated as "Abnormal" the investigator should document the specific abnormality.

#### **6.4.8 Vital signs**

##### **6.4.8.1 Pulse and blood pressure**

One pulse measurement will be taken after the patient has been sitting and resting for at least 5 minutes and before blood samples are taken. The pulse measurement will be followed by three blood pressure (BP) measurements separated by 2 minutes each. All three BP readings should be recorded. At Visit 1 the seated BP will be recorded three times in both the left and the right arms. All three measurements should be made in one arm before transferring the cuff to the other arm. The arm with the highest mean seated BP readings will be the one used for all subsequent readings throughout the study. BP readings should be taken while the patient is in a comfortable seated position with the arm supported at the level of the heart. All readings should be recorded. Ideally, blood pressure should be measured with the same machine, at the same time of day, and by the same personnel at each visit. A standard mercury sphygmomanometer with a standardised cuff adapted to the size of the patient's arm is recommended. Oscillometric devices (such as Dynamap) may be used at sites where:

- a mercury sphygmomanometer is not available, or

- a mercury sphygmomanometer is available, but site staff is not practiced in its use
- use of mercury devices is restricted by local law.

New oscillometric devices must be recalibrated when the certificate of calibration provided by vendor expires. Thereafter the devices must be calibrated with a frequency according to local regulation but at least annually and calibration must be documented. Aneroid devices should not be used.

At each visit, three blood pressure (BP) measurements separated by 2 minutes each will be done. All three BP readings should be recorded and entered in eCRF.

#### **6.4.8.2 Orthostatic blood pressure**

At selected visits where orthostatic BP and pulse are collected, supine and standing measurements should be made after the seated BP and pulse measurements have been made, using the same arm that was used for the seated BP measurements. All readings should be recorded. Ideally, blood pressure should be measured with the same machine, at the same time of day, and by the same personnel at each visit.

##### **Supine BP and pulse**

The supine BP and pulse must be measured prior to the standing BP and pulse. After the patient rests in the supine position for at least 5 minutes, supine BP and pulse will be determined from three replicate measurements obtained at least 1 minute apart. All three readings must be recorded.

##### **Standing BP and pulse**

After the supine BP and pulse measurements are obtained, the patient will stand for 2 to 3 minutes. After this time, the BP will be measured with the arm supported at the level of the heart. Standing BP and pulse will be determined from three replicate measurements obtained at least 1 minute apart. All three readings must be recorded.

If a new occurrence of previously absent orthostatic hypotension is demonstrated, it should be recorded in the appropriate section of the CRF. The investigator may consider to reduce concomitant anti-hypertensive medication to alleviate signs and symptoms of orthostatic hypotension, without discontinuation of investigational product. Refer to Section [5.6.2.5](#).

#### **6.4.9 Other safety assessments**

Self-monitored plasma glucose readings and hypoglycaemic events will be collected in a patient diary and reviewed by the investigator at each visit. The investigator will also ask the patient about symptoms of urinary tract and genital infections at every scheduled visit starting at Visit 4.

#### 6.4.9.1 Fasting plasma glucose concentrations and hypoglycaemic events

Patient self-monitoring of FPG is performed in order to reduce the risks associated with prolonged hyperglycaemia and to confirm symptoms of hypoglycaemia. Patients will be asked to perform self-monitoring of FPG using a glucometer provided by AstraZeneca. The patients will receive instructions for the use of the glucometer according to the manufacturer's instructions.

FPG should be self-monitored at least every second day between visits 2 and 9 and at least once a week between visits 9 and 17. The results should be recorded in the patient diary, which will be collected and reviewed by the study personnel at each visit starting with Visit 3; a print-out will be stored in the investigator study file. A new diary will be dispensed to the patient at each of these visits.

The memory of the glucometer should be reviewed and compared with the readings in the patient's diary. The glucose values should be reviewed by the study personnel to identify any unusually high or low values, and to confirm that self-monitoring was performed by the patient. If fingerstick glucose values are discordant with central laboratory results or with clinical symptoms, the patient's glucometer should be tested and the glucometer instructions should be re-reviewed with the patient.

Glycaemic rescue criteria and relevant procedures are described in Section 5.6.2.

#### Hypoglycaemic events

The patients will be asked to always check their blood glucose if they develop symptoms suggestive of hypoglycaemia and to record specific symptoms in the patient diary.

A hypoglycaemic event can be either:

- Symptoms of hypoglycaemia with a low blood glucose reading
- A low blood glucose reading
- Symptoms of hypoglycaemia without a blood glucose reading

For the evaluation of hypoglycaemic events, this study will use the definitions provided in the CPMP guidance on clinical investigation of medicinal products in the treatment of diabetes mellitus, as described below.

- **Major hypoglycaemic events**, defined as symptomatic events requiring external assistance due to severe impairment in consciousness or behaviour, with a capillary or plasma glucose value <54 mg/dL (<3.0 mmol/L), and prompt recovery after glucose or glucagon administration.

- **Minor hypoglycaemic event**, defined as either a symptomatic event with a capillary or plasma glucose value  $<63$  mg/dL ( $<3.5$  mmol/L) but  $>54$  mg/dL ( $3.0$  mmol/L), and no need for external assistance, or an asymptomatic blood glucose measurement  $<63$  mg/dL ( $<3.5$  mmol/L).
- **Events suggestive of hypoglycaemia**, defined as a symptomatic event without a confirmatory blood glucose measurement.

If the patient experiences symptoms suggestive of hypoglycaemia and has an associated capillary or plasma glucose value  $\geq 63$  mg/dL ( $\geq 3.5$  mmol/L), the event should be recorded as an adverse event rather than as a hypoglycaemic event. If the physician does not consider the glucose measurement to be accurate, however, the event should be documented as a hypoglycaemic event in the hypoglycaemia eCRF.

Data to be collected for each hypoglycaemic event:

- Date and time of episode (start and stop)
- Whether the patient was sleeping at the time of the event
- Whether symptoms were present, and list of symptoms
- Possible contributing factors
- Whether a fingerstick value was obtained, and if so, the plasma glucose value
- Whether intervention was needed for recovery
- How the episode was treated
- Whether recovery was prompt after treatment
- Time of last anti-hyperglycaemic drug administration
- Time of last meal

The patient diary will be reviewed and the hypoglycaemic event data will be transcribed into the eCRFs at each clinical visit. A new diary for the next period will be handed over to the patient if needed. If a major hypoglycaemic event or more than one minor event has occurred since the previous visit, the patient should contact the investigator. For recording of hypoglycaemic events/symptoms suggestive of hypoglycaemic events as AEs, see Section [6.4.3](#).

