### **Development of any study specific criteria for discontinuation:**

8. Treatment with glucocorticoids equivalent to oral prednisolone >10 mg/day (two temporary periods of higher daily doses for no longer than 7 days each are allowed)
9. Major and/or frequent hypoglycaemic events, defined as  $\geq 1$  major event or recurring minor events (See 6.4.9.1 for definition of minor and major). This definition should be applied after possible contributing factors (eg, excessive physical activity) have been excluded by the investigator

10. Pregnancy confirmed by a positive pregnancy test or otherwise verified
11. Change in kidney function (Please see [Appendix K](#) for further guidance):
  - For all patients treated with metformin: calculated creatinine-clearance <60 mL/min or an increase in serum creatinine of  $\geq 44 \mu\text{mol/L}$  ( $\geq 0.5 \text{ mg/dL}$ ) above the baseline value confirmed by a repeated measurement within one week.
  - For patients not treated with metformin: a) calculated creatinine clearance <60 ml/min or b) in subjects with baseline creatinine  $\geq 123 \mu\text{mol/L}$  ( $\geq 1.4 \text{ mg/dL}$ ) an absolute increase in serum creatinine of  $\geq 88 \mu\text{mol/L}$  ( $\geq 1.0 \text{ mg/dL}$ ), or c) in subjects with baseline creatinine <123  $\mu\text{mol/L}$  (<1.4 mg/dL) an absolute increase in serum creatinine of  $\geq 44 \mu\text{mol/L}$  ( $\geq 0.5 \text{ mg/dL}$ ).
12. CK >10x ULN confirmed at a repeated measurement preferably within 24 hours, but not exceeding 72 hours, see Section [5.8.1](#)
13. Patients with a central laboratory ALT and/or AST >3x ULN will be scheduled for a follow-up visit within 3 days following the receipt of the result. See [Appendix J](#) for further guidance. Patients should be discontinued from treatment if the initial **and** repeated laboratory tests meet any of the following criteria:
  - ALT and/or AST are >3x ULN **and** TB>1.5x ULN
  - ALT and/or AST are >5x ULN for  $\geq 14$  consecutive days, at any time after initial confirmatory results
  - ALT and/or AST are >8x ULN.
14. Serum Sodium  $\leq 125 \text{ mmol/L}$  with or without symptoms; see [Appendix I](#) for further guidance

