### **Hypoglycaemic events**

A separate section in the eCRF will be used to document all reported episodes of hypoglycaemia. Hypoglycaemic episodes or discontinuation due to hypoglycaemia should not be reported on the AE eCRF page unless the event fulfils protocol criteria for a Serious Adverse Event (see Section [6.4.2](#)). In this case, an SAE must be reported in addition to the

hypoglycaemia eCRF pages for hypoglycaemia. The Investigator is responsible for questioning the patient about all symptoms reported in the diary and for determining if they meet the clinical definition of hypoglycaemia. Only symptoms and/or blood glucose values deemed by the Investigator to meet the definition of hypoglycaemia should be reported on the hypoglycaemia eCRF pages (see Section 6.4.9.1).

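### The three hypoglycaemia classes in Section 6.4.9.1 are not exhaustive: symptomatic self-treated events at or below 54 mg/dL, and some assisted events, belong to none of them

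*Supplement*

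**What the plan says.** Section 6.4.9.1 begins with a broad description. One of its three routes to a hypoglycaemic event is "Symptoms of hypoglycaemia with a low blood glucose reading", with no number attached to low. It then states that events will be evaluated with definitions taken from CPMP guidance, and gives three:

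- **Major:** "symptomatic events requiring external assistance due to severe impairment in consciousness or behaviour, with a capillary or plasma glucose value <54 mg/dL", together with prompt recovery after glucose or glucagon.
- **Minor:** "defined as either a symptomatic event with a capillary or plasma glucose value" below 63 but above 54 mg/dL "and no need for external assistance, or an asymptomatic blood glucose measurement" below 63 mg/dL. The asymptomatic limb has no lower bound.
- **Suggestive:** "defined as a symptomatic event without a confirmatory blood glucose measurement".

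Symptoms with a reading of 63 mg/dL or more are recorded as an adverse event instead, unless the physician doubts the reading. There is no residual class.

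Four other places bear on the point:

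- Section 6.4.3 keeps non-serious hypoglycaemia off the adverse event page and adds: "Only symptoms and/or blood glucose values deemed by the Investigator to meet the definition of hypoglycaemia should be reported on the hypoglycaemia eCRF pages".
- Section 5.8, item 9, lists "Major and/or frequent hypoglycaemic events" as a discontinuation criterion and spells this out as one or more major events or recurring minor events, citing Section 6.4.9.1.
- The end of Section 6.4.9.1 asks the patient to contact the investigator after a major event or more than one minor event since the last visit.
- Section 11.2.2 tabulates patients with one or more hypoglycaemic episodes up to week 24, without reference to class.

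**The concern.** Classes used to evaluate a safety outcome should place every event once. Here the symptomatic limb of minor stops above 54 mg/dL, while major takes over below 54 mg/dL only when someone else had to help. A patient who has symptoms, measures 50 mg/dL and treats the episode alone falls between the two.

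Hypoglycaemic events are a named safety outcome in a population that may be on insulin or a sulfonylurea. A table by class would leave out the lowest readings among symptomatic self-treated events, and so could misstate how severe confirmed hypoglycaemia was in each arm. Item 9 of Section 5.8 and the patient-contact rule are worded in the same class terms, so the gap passes into them as well.

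**Working it through.** No sample size, power or alpha figure is involved. The check is to apply the written definitions to every combination of symptoms, external assistance, glucose and prompt recovery. All inputs come from Section 6.4.9.1.

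Rules as written, with g the glucose value in mg/dL:

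- Major: symptomatic, assisted, g < 54, prompt recovery.
- Minor, symptomatic limb: symptomatic, unassisted, 54 < g < 63.
- Minor, asymptomatic limb: asymptomatic, g < 63.
- Suggestive: symptomatic, no reading.
- Adverse event page: symptomatic, g ≥ 63.

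Results:

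| Glucose (mg/dL) | Symptomatic, self-treated | Symptomatic, assisted | Asymptomatic |
|---|---|---|---|
| none | suggestive | suggestive | not an event |
| 40, 53 | **no class** | major if recovery prompt, otherwise **no class** | minor |
| 54 | **no class** | **no class** | minor |
| 55, 62 | minor | **no class** | minor |
| 63 | adverse event | adverse event | not an event |

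Four things follow.

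1. There are three gaps: symptomatic self-treated events at g ≤ 54, assisted symptomatic events at 54 ≤ g < 63, and assisted events at g < 54 without prompt recovery.
2. The ordering is inconsistent. A reading of 40 mg/dL without symptoms is minor; the same reading with symptoms and self-treatment has no class.
3. The gap is not a unit artefact. 54 / 18.016 = 3.00 mmol/L and 63 / 18.016 = 3.50 mmol/L, which agree with the mmol/L values printed beside them. A reading of exactly 54 is excluded by both strict inequalities.
4. The rules built on the classes inherit the gap. Read literally, repeated symptomatic self-treated readings of 50 mg/dL count toward neither item 9 of Section 5.8 nor the patient-contact rule, whereas repeated readings of 60 mg/dL count toward both.

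On recording, two readings of Section 6.4.3 are possible. If the definition it refers to is the broad description at the head of Section 6.4.9.1, an unclassified event goes on the hypoglycaemia page and enters the count in Section 11.2.2. If it is taken to mean the three classes, the event meets none, and the adverse event page is closed to it unless it is serious. It could then be recorded nowhere.

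**The case against.** The strongest reply is that nothing the protocol plans to count is truncated. The one tabulation it specifies, in Section 11.2.2, is of any episode, and a symptomatic 50 mg/dL meets the broad description of an event. Glucose value, symptoms, treatment and recovery are all collected, so the class can be rebuilt later. Class tables would be specified in the SAP, which is not among the documents available. This largely stands. A reader might infer that the overall hypoglycaemia count is cut short or that data are lost; the documents do not support that, provided investigators use the broad description. What remains is that Section 6.4.9.1 itself adopts the three classes for evaluation, and an any-episode count cannot show severity.

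A second reply is that patient safety does not rest on the class label. Section 5.6.2.3 requires review of any hypoglycaemia confirmed clinically or by laboratory value, Section 5.6.2.2 ties insulin reduction to glucose readings rather than classes, and Section 5.8 allows discontinuation for an adverse event or judged risk. This also stands, and it limits the consequence. It does not make item 9 or the contact rule consistent with the definitions.

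Third, the definitions are attributed to CPMP guidance, so the gap may have been adopted knowingly. That source cannot be checked here. Its origin would not make the list exhaustive as written in this protocol.

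Two further inferences go too far. Not every assisted event at 54 mg/dL or above lacks a class, because readings of 63 mg/dL or more go to the adverse event page. Nor are all readings at or below 54 mg/dL unclassified, because asymptomatic ones are minor.

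**Conclusion.** The definitional gap is real and follows from the text alone. Its consequence is confined to reporting by class, to a possible recording ambiguity, and to two rules that borrow the class terms. The any-episode count is intact if these events are recorded under the broad description.

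The number of events affected cannot be stated. The documents give no event rate and no glucose distribution. Any assumed share of symptomatic self-treated events below 63 mg/dL that lie at or below 54 mg/dL simply returns itself as the unclassified share of those events: assume 20% to 50% and the answer is 20% to 50%. The finding does not depend on such a figure, and nothing in the documents shows that the gap favours either blinded arm.

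No primary or key secondary endpoint is affected. The point should be corrected because the rule as stated leaves events unplaced and the repair is cheap, but it does not threaten the trial's main conclusions.

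**What to change.** For recording and reporting only, settled before unblinding (under Section 5.4.1 only patients and investigators stay blinded after the 24-week period):

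1. State in Sections 6.4.3 and 6.4.9.1 that every event meeting the broad description goes on the hypoglycaemia page, whether or not it fits a named class.
2. Derive exhaustive, mutually exclusive reporting categories from glucose, symptoms, assistance and recovery. Keep the existing classes as defined and add separate lines for (a) symptomatic, unassisted events at 54 mg/dL or lower and (b) assisted events with a reading below 63 mg/dL that do not meet the major definition. Assisted events with no reading stay in suggestive, so no event is counted twice.
3. Confirm that the collected item on whether intervention was needed separates external assistance from self-treatment. Section 6.4.9.1 lists that item and how the episode was treated, but names neither as external assistance. If it does not separate them, the form needs a small change.
4. Reconcile item 9 of Section 5.8 and the patient-contact rule with the definitions they cite. Which events should trigger either rule is a clinical decision, and none is proposed here.

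Simply dropping the lower bound of the symptomatic minor limb is not recommended. It would change who meets item 9 and would leave the assisted events unplaced.

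The cost is wording and a programming rule on fields that are mostly collected already. The reported categories would depart slightly from the guidance definitions the protocol cites; keeping the original three lines visible in the table limits that.
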